**Table 3 Clinical Laboratory Tests**

Category	Parameters
Hematology	Hematocrit, hemoglobin, platelets, RBC count, WBC count with differential (bands, basophils, eosinophils, lymphocytes, monocytes, neutrophils), and ANC
Chemistry	
Screening/Baseline/ End-of-Treatment Panel	Pregnancy test (serum $\beta$ -hCG), LDH, chloride, potassium, sodium, BUN, serum creatinine, phosphorus, calcium, albumin, total protein, alkaline phosphatase, ALT, AST, total bilirubin, CPK, TSH, and free T 4 in the case of abnormal TSH
Treatment Panel	Chloride, potassium, sodium, BUN, serum creatinine, phosphorus, calcium, albumin, total protein, alkaline phosphatase, ALT, AST, total bilirubin, CPK Serum TSH, free T 3 , and free T 4 , and in the case of abnormal TSH: anti-thyroglobulin antibodies and anti-thyroid peroxidase antibodies
Urinalysisa	Glucose, protein, leukocytes, nitrites, ketones, bilirubin, blood, urobilinogen, pH, and specific gravity. Microscopic examination of sediment to include: bacteria, casts, crystals, epithelial cells, RBCs, and WBCs Urine pregnancy test (Cycle 1 Day 1 only)

ALT = alanine aminotransferase, ANC = absolute neutrophil count, AST = aspartate aminotransferase,  $\beta$ -hCG = beta human chorionic gonadotropin, BUN = blood urea nitrogen, LDH = lactate dehydrogenase, RBC = red blood cell, T3 = triiodothyronine, T4 = thyroxine, TSH = thyroid-stimulating hormone, WBC = white blood cell, CPK = creatine phosphokinase.

a: When a local laboratory is required for a urinalysis, a Urinalysis Reagent Test Strip (URS-10) may be used.

Clinical laboratory tests will be performed by a central laboratory. All blood and urine samples will be collected and sent to the central laboratory on the day of collection unless otherwise instructed. In cases of a safety concern, blood samples will be split, or two samples drawn, to allow a local laboratory analysis in addition to the central laboratory.

All hematology, blood chemistry (including pregnancy test, as applicable), and urinalysis samples are to be obtained before study drug administration and results reviewed before administration/dispensing of study drug at the beginning of each treatment cycle. Refer to [Table 1](#) for dose interruption and reduction instructions in the event of clinically significant laboratory abnormalities.

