a: **Pretreatment:** Screening up to 28 days before start of treatment except for signing of the ICF which may be up to 8 weeks before the first dose of study drug; Baseline up to 7 days before start of treatment. If Screening laboratory tests (Hematology, Chemistry, and serum pregnancy) are performed within 7 days prior to Cycle 1 Day 1, these tests may count as Baseline tests and need not be repeated at Baseline. If Baseline central laboratory test results are not available in time to confirm eligibility, the local site laboratory results (including from Cycle 1 Day 1) may be used for this purpose.

**Treatment:** cycles of 21 days, up to 8 cycles; applicable to the Lead-in only, if subject is treated beyond Cycle 8 per protocol, the same assessments should be performed as for Cycles 1 to 8; however, no PK samples will be collected after Cycle 8.

**Extension:** Up to 3 years.

**Day 8 Assessments:** Day 8 assessments are required in cycles 1-3, and are optional on cycle 4 and beyond.

**EOT:** Tumor assessments are only required at EOT if they affect GRS. Other EOT tests (with the exception of serum pregnancy test, and QoL) need only be performed if the EOT visit is > 7 days from the most recent Cycle Day 1 visit.

- b: A biopsy sample will be sent to a central laboratory for testing of CD25 expression by IHC. The sample may be sent in formalin, or may be a formalin fixed paraffin embedded (FFPE) sample block, or may be sent as slides (minimum of five slides). Results must be obtained before enrollment of subject in the study. Results obtained at Screening or from an archival tumor biopsy ( $\leq 6$  months) can be used as long as the test was performed by the study-designated central laboratory. Multiple lesions may be tested. Re-biopsy with selection of the most representative lesion is required if the subject had disease progression or relapse since the last biopsy, or had received anticancer therapy since the last biopsy.
- c: Blood sampling, if blood assessment required for CTCL diagnosis; whole blood to be collected for flow cytometry analysis by central laboratory. Lymph node biopsy (if required per [Olsen 2011](#)): allow either fine needle aspirate or core biopsy; if additional lymph node analysis is required, surgical biopsy may follow, if required for CTCL diagnosis and/or staging; lymph node analysis to be performed by local site laboratory.

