- h: Chemistry laboratory tests should include the following thyroid function tests: serum TSH, free T3, free T4, and if these are abnormal, then include anti-thyroglobulin antibodies and anti-thyroid peroxidase antibodies (reflex testing at central laboratory only). Laboratory tests should also include serum  $\beta$ -hCG and LDH (screening only), chloride, potassium, sodium, BUN, serum creatinine, phosphorus, calcium, albumin, total protein, alkaline phosphatase, ALT, AST, total bilirubin, and CPK. Hematology laboratory tests include hematocrit, hemoglobin, platelets, RBC count, WBC count with differential (bands, basophils, eosinophils, lymphocytes, monocytes, neutrophils), and ANC. If Screening laboratory tests (Hematology, Chemistry, and serum pregnancy) are performed within 7 days prior to Cycle 1 Day 1, these tests may count as Baseline tests and need not be repeated at Baseline. On Day 1 of each cycle, laboratory assessments (local site laboratory) must be reviewed prior to drug administration, in addition to submitting to the central lab. For Cycle Day 8, a window of  $\pm 1$  day is allowed.

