### 9.5.8 Completion/Discontinuation of Subjects

See [Section 9.3.3, Removal of Subjects from Therapy or Assessment](#), for reasons allowed for discontinuation.

All subjects who discontinue early from the study treatment are expected to complete the EOT procedures indicated on the Schedule of Procedures/Assessments (see [Table 4](#)), if possible.

For all subjects who discontinue from the study, study disposition information will be collected on the appropriate eCRF.

A subject who has ceased to return for visits will be followed up by mail, phone, or other means as much as possible to gather protocol-specified follow-up information.

Subjects who are not evaluable for DLT in Cycle 1 should be replaced.

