6.7.3 Laboratory Values

Laboratory results will be summarized using Système International (SI) units, as appropriate.

On-treatment laboratory tests will be defined as laboratory tests conducted from the start of treatment to no more than 30 days after the last dose of study treatment. Central laboratory test results will be primary data source for laboratory analyses. Only when the central laboratory tests results are missing, the local laboratory test results will be used as substitute.

For all quantitative parameters listed in Table 3 (protocol Section 9.5.4.3) the actual value and the change from baseline to each postbaseline visit and to the end of treatment (defined as the last on treatment value) will be summarized by visit using descriptive statistics. Qualitative parameters listed in Table 3 (protocol Section 9.5.4.3) will be summarized using frequencies (number and percentage of subjects), and changes from baseline to each postbaseline visit and to end of treatment will be reported using shift tables. Percentages will be based on the number of subjects with both nonmissing baseline and relevant postbaseline results.

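### From Cycle 4 on, the end-of-treatment laboratory waiver is tied to Cycle Day 1 and not to the last dose, so a subject who stops within that week may have no required hematology or chemistry after the final infusions

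*Protocol*

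**What the plan says.** Protocol 9.5.5.1 (Table 4, footnote a) limits the EOT tests other than tumor assessments: they "need only be performed if the EOT visit is > 7 days from the most recent Cycle Day 1 visit". Protocol 9.5.5.2 repeats the rule. The pregnancy test and the quality-of-life questionnaires are exempt from it; hematology and chemistry are not.

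On Day 1 sampling, Protocol 9.5.4.3 says: "All hematology, blood chemistry (including pregnancy test, as applicable), and urinalysis samples are to be obtained before study drug administration". Footnote h agrees: "On Day 1 of each cycle, laboratory assessments (local site laboratory) must be reviewed prior to drug administration". Under Protocol 9.4.1, E7777 is infused on five consecutive days of each 21-day cycle.

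The only other scheduled on-treatment time for these tests is Day 8, and footnote a says of it: "Day 8 assessments are required in cycles 1-3, and are optional on cycle 4 and beyond". Table 4 shows no hematology or chemistry on Days 2 to 5 or in Follow-Up. Protocol 9.5.8 adds: "All subjects who discontinue early from the study treatment are expected to complete the EOT procedures", pointing to Table 4, so the waiver applies to early stops as well.

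SAP 6.7.3 summarises laboratory change from baseline to each visit and to "end of treatment (defined as the last on treatment value"). On-treatment there runs from the start of treatment to 30 days after the last dose.

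**The concern.** The waiver lets the latest Cycle Day 1 results stand in for the EOT results. That is sound if the subject was not dosed after those samples. It is not sound if infusions followed, because the Day 1 sample then says nothing about their effect.

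Stops for acute toxicity can easily fall in this window. Protocol 9.1.2 defines infusion reactions as occurring within 24 hours of an infusion, and some rows of Table 1 call for immediate permanent discontinuation. With dosing on Days 1 to 5, such a stop falls early in the cycle. The documents set no window for the EOT visit, so a visit by Day 8 is allowed.

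The tests concerned matter for this drug. Serum albumin is one of the three components of the capillary leak definition in Protocol 9.1.2, and Amendment 05 added CPK monitoring after a fatal rhabdomyolysis report. Without a later sample, a change caused by the final infusions may go unrecorded, and an end-of-treatment summary may show a value that precedes them.

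**Working it through.** The plan states no figure to reproduce. The check enumerates the schedule.

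**Inputs**
- Infusions on Days 1 to 5 of a 21-day cycle (Protocol 9.4.1).
- Day 1 hematology and chemistry before dosing (Protocol 9.5.4.3; footnote h).
- Day 8 laboratory tests required in Cycles 1 to 3 and optional afterwards (footnote a).
- EOT tests required only if the visit is more than 7 days after the latest Cycle Day 1 (footnote a; 9.5.5.2).

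**Step 1: which EOT days are waived.** Let d be the cycle day of the EOT visit. The tests are waived if d − 1 ≤ 7, that is d ≤ 8. Once a dose has been given in the cycle, the days that matter are 2 to 8.

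**Step 2: how far the waiver reaches past the last dose.** If the last dose is on Day k with no infusion missed, k infusions follow the Day 1 sample, and the waiver reaches 8 − k days beyond the last dose.

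| Last dose (k) | Infusions after the Day 1 sample | Waiver reaches (days after last dose) |
|---|---|---|
| Day 1 | 1 | 7 |
| Day 2 | 2 | 6 |
| Day 3 | 3 | 5 |
| Day 4 | 4 | 4 |
| Day 5 | 5 | 3 |

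**Step 3: which cycles have the gap.**
- If Day 8 tests still apply after a stop, Cycles 1 to 3 are covered. The gap is in Cycles 4 to 8, which is 5 of 8 planned cycles, and in any later cycle.
- If the EOT visit replaces Day 8, the gap is in all 8. The documents do not state this. Protocol 9.3.3 and 9.5.8 refer early discontinuers to off-treatment visits and EOT procedures without mentioning Day 8.

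**Step 4: two examples.**
- Cycle 5, last dose Day 3, EOT visit Day 6: 6 − 1 = 5 ≤ 7, so the tests are waived. Three infusions follow the last required sample.
- Eight full cycles without delay, EOT visit by Cycle 8 Day 8: the last required sample is pre-dose on study day 1 + 7 × 21 = 148. Five of 8 × 5 = 40 infusions (12.5%) follow it. This needs an EOT visit within three days of the Day 5 infusion.

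**Step 5: what the SAP does.** If no later sample exists, the last on-treatment value is the pre-dose Day 1 result, and it is summarised as end of treatment. Such a subject does not vanish from the laboratory tables. Anyone dosed in Cycle 4 should have six required post-baseline sets: Day 8 of Cycles 1, 2 and 3, and Day 1 of Cycles 2, 3 and 4. What is missing is any view of the final doses.

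**The case against.** The other side has several good points.

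- **The early cycles are covered.** A reader might infer that a subject stopping in Cycle 1 has no post-baseline laboratory value. Day 8 tests are required in Cycles 1 to 3, and no text drops them after a stop. That inference needs a missed visit or a rule the documents do not contain.
- **Few subjects may fall in the window.** Most toxicity rows in Table 1 call for interruption. Discontinuation for a toxicity delay comes only after more than 21 days, when an EOT visit would normally be outside the waiver. Many immediate stops would be serious events, which Protocol 9.5.7.1 follows to resolution or stabilization.
- **Other samples may exist.** Protocol 9.4.1.3 lists tests before administration with a Day 1 restriction that may attach only to renal function. On that reading albumin, liver tests, blood count and CPK precede every infusion. The same section requires CPK if capillary leak is suspected, and 9.5.4.3 provides for local analysis when there is a safety concern. SAP section 9 counts unscheduled visits in worst post-baseline analyses.
- **The waiver has a purpose.** It avoids near-duplicate tests, suits a subject stopped at Day 1 without dosing, and sets a minimum only.

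These points limit the size of the problem but do not remove it. A test before each infusion still precedes the last one. The CPK trigger covers one analyte and depends on suspicion. Event follow-up and unscheduled sampling do not require a panel after the last dose.

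A reader might also infer that the EOT examination and ECG are waived. The documents do not settle this. Footnote e calls for a complete examination at study termination, and footnote f lists an EOT ECG, neither with the 7-day condition. That is a conflict with footnote a to reconcile.

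**Conclusion.** The point holds from Cycle 4 onward: 5 of the 8 planned cycles and any later cycle. There, an EOT visit on Days 2 to 8 can follow one to five infusions with no required hematology or chemistry after the last dose. SAP 6.7.3 can then present a pre-dose value as end of treatment. For Cycles 1 to 3 it is only an open question whether the Day 8 tests survive discontinuation.

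The conclusion rests on the schedule as written, and on the EOT visit taking place by Day 8, which the documents allow but do not require. An EOT visit on Day 9 or later restores the tests.

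A reader might go further and conclude that the laboratory tables understate toxicity by some definite amount. The documents give neither the share of subjects who stop in this window nor their risk of an abnormality, and some values may be captured by unscheduled sampling. The direction is plausible, because the missing values would belong partly to subjects stopping for acute toxicity. The size cannot be stated.

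**What to change.** 1. In footnote a and Protocol 9.5.5.2, allow EOT laboratory tests to be omitted only if no E7777 was given after the most recent Cycle Day 1 samples.
2. State whether the Day 8 laboratory tests of Cycles 1 to 3 still apply once a subject has discontinued.
3. Reconcile footnote a with footnotes e and f on the EOT examination and ECG.
4. In SAP 6.7.3, do not label a value taken before the last dose as end of treatment, and report the number of subjects with no laboratory value after their last dose.

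The cost is one routine panel, already listed in Table 4, for the few subjects whose EOT visit falls on Days 2 to 8. The SAP change needs no new data and would show how often the gap occurred.

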### 9.5.5 Schedule of Procedures/Assessments

#### 9.5.5.1 Schedule of Assessments

PHASE a	PRETREATMENT		TREATMENT							Follow-Up	
	Period a	Screening	Baseline	Cycles 1 to 8 (Cycle 9 and beyond, if applicable) a							
	Cycle Day	Up to -28	Up to -7	1	2	3	4	5	8		EOT a
Procedures/Assessments											
Informed consent		X									
Medical history		X									
Inclusion/exclusion		X									
Tumor biopsy for CTCL diagnosis b		X									
Blood sampling or lymph node biopsy for CTCL diagnosis c		X									
Prior/concomitant medications d		X	X	X						[X]	
Vital signs e			X	X	X	X	X	X	[X]	[X]	
Physical examination and ECOG e			X	X						[X]	
ECG f		X		X						[X]	
Urine pregnancy test g				X							
Urinalysis g			X	X					[X]		
Serum β-hCG pregnancy test h		X	X							X	
Hematology laboratory tests h		X	X	X					[X]	[X]	
Chemistry laboratory tests h		X	X	X					[X]	[X]	
PK and Immunogenicity blood samples i				[X]							[X]
Drug administration: E7777 j				X	X	X	X	X			
Tumor assessment: skin mSWAT with photography k		X		X						[X]	[X]
Tumor assessment: lymph node PE k		X		X						[X]	[X]
Tumor assessment: blood disease k		X		X						[X]	[X]
Patient-reported pruritus assessment l		X		X						[X]	[X]

Table 4 Schedule of Assessments										
PHASE a	PRETREATMENT		TREATMENT							Follow-Up
Period a	Screening	Baseline	Cycles 1 to 8 (Cycle 9 and beyond, if applicable) a							
Cycle Day	Up to -28	Up to -7	1	2	3	4	5	8	EOT a	
Procedures/Assessments										
CT scans m	X					[X]				[X]
Adverse event n		X				X				X
Survival o										X
QoL p		X	X							X

Table 4 Schedule of Assessments (cont'd)									
PHASE a	EXTENSION								Follow-Up q
Period a	Treatment (Continued treatment after data cut-off) a								
Cycle Day	1	2	3	4	5	8	EOT a		
Procedures/Assessments									
Prior/concomitant medications d				X					[X]
Vital signs e	X	X	X	X	X		[X]		[X]
Physical examination and ECOG e	X								[X]
ECG f	X								[X]
Urine pregnancy test g	X								
Urinalysis g	X						[X]		

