Serum β-hCG pregnancy test h									X
Hematology laboratory tests h	X						[X]		[X]
Chemistry laboratory tests h	X						[X]		[X]
PK and Immunogenicity blood samples i	[X]								[X]

Table 4 Schedule of Assessments (cont'd)								
PHASEa	EXTENSION							
Perioda	Treatment (Continued treatment after data cut-off)a							Follow-Upa
Cycle Day	1	2	3	4	5	8	EOTa	
Procedures/Assessments								
Drug administration: E7777 j	X	X	X	X	X			
Tumor assessment: skin mSWAT with photography k	X						[X]	[X]
Tumor assessment: lymph node PE k	X						[X]	[X]
Tumor assessment: blood disease k	X						[X]	[X]
Patient-reported pruritus assessment l	X						[X]	[X]
CT scans m				[X]			[X]	[X]
Adverse event n				X			X	X
Survival o								X
QoL p	[X]						X	X

ALT = alanine aminotransferase, ANC = absolute neutrophil count, AST = aspartate aminotransferase, β-hCG = beta-human chorionic gonadotropin, BUN = blood urea nitrogen, CR = complete response, CRM = Continual Reassessment Method, CS = Color Distortion test, CT = computed tomography, CTCL = cutaneous T-cell lymphoma, ECG = electrocardiogram, ECOG = Eastern Cooperative Oncology Group, EOT = End of Treatment, FFPE = formalin-fixed paraffin embedded, IHC = immunohistochemistry, i.v. = intravenous, LDH = lactate dehydrogenase, min = minutes, mSWAT = modified Severity Weighted Assessment Tool, N/A = Not applicable, PD = progressive disease, PE = physical examination, PR = partial response, QoL = quality of life, RBC = red blood cell, TSH = thyroid-stimulating hormone, WBC = white blood cell  
Note: [X] = Either: not required in all cycles, or not required in all subjects. See footnotes.

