- d: Concomitant medications to be reviewed at every visit, until 30 days after the last treatment dose. Use of topical or systemic steroids within 14 days of Cycle 1 Day 1 is not allowed, with the exception noted under “Concomitant Medications” (see [Section 9.4.7](#)).
- e: Vital signs measured at baseline and EOT (if necessary), and on drug treatment days and on Cycle Day 8 ( $\pm 1$  day), before and at the end of the infusion and 30 minutes after infusion. A complete physical examination will be performed at Baseline, Day 1 of each cycle, and at Study Termination (discontinuation from study). A symptom-directed examination will be performed on all other visit days. All physical examinations are to include monitoring of weight and blood pressure as signals for potential vascular leak syndrome.
- f: Single 12-lead ECGs will be performed during Screening, on Day 1 of each cycle and at End of Treatment.
- g: On Cycle Day 1 (i.e. treatment day), urinalysis will be performed prior to study drug administration. Urinalysis includes glucose, protein, leukocytes, nitrites, ketones, bilirubin, blood, urobilinogen, pH, and specific gravity. Microscopic examination of sediment includes bacteria, casts, crystals, epithelial cells, RBCs, and WBCs. When a local laboratory is required for a urinalysis, a Urinalysis Reagent Test Strip (URS-10) may be used. On Cycle 1 Day 1 only: a urine pregnancy test will be performed prior to study drug administration.

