- i: Blood sampling for pharmacokinetic (PK) and immunogenicity (anti-E7777, anti-IL-2, and neutralizing antibodies) testing. Sample volumes are 3 mL for PK assessments and 3 mL for immunogenicity testing. Pharmacokinetic assessment of E7777 will be performed in all subjects in the Lead-In part and in the first 12 subjects in Main Study. Serial blood samples will be taken on Day 1 of Cycles 1, 3, and 5, with sparse sampling in Cycle 8. Serial blood samples will be collected at predose, 30 min after the start of the infusion, end-of-infusion, and 30, 60, 90, 120, 180, 240, and 300 minutes after the end of the infusion. Sparse samples will be collected at predose, end-of infusion and between 60 and 180 min after the infusion ends. For the remaining subjects in the Main Study, sparse blood samples will be taken on Day 1 of Cycle 1. They will be collected at predose, end-of infusion and between 60 and 180 min after the end of the infusion. Immunogenicity will be assessed in all subjects in both the Lead-In part and the Main Study. A predose blood sample for immunogenicity assessment will be collected prior to dosing on Day 1 in Cycles 1, 2, 3, 5, and 8; after that, all subjects will be followed up for immunogenicity testing for anti-IL2 at 6 months, one year and every year thereafter until antibody titers decrease to baseline level. These blood samples will be collected before study drug administration.
- j: E7777 by i.v. infusion over 60 minutes ( $\pm 10$  minutes). Premedication required in Cycles 1 to 3 (see protocol). Lead-In: E7777 at a dose assigned according to the CRM; Main Study: E7777 at a dose determined in the Lead-In. A window of  $\pm 1$  day is allowed for start of treatment cycle from Cycle 3 onward, inclusive.
- k: Assessment of skin disease by mSWAT score, lymph node disease by physical examination, and blood disease by flow cytometry (central laboratory). During the Extension phase, assessment is to be performed every 4 weeks ( $\pm 1$  week) for 1 year after end of study treatment, then every 12 weeks ( $\pm 3$  weeks) thereafter for up to 3 years, or sooner if clinically indicated. In addition, skin assessments as needed for the supplemental alternate method for independent review using the method of [Prince \(2010\)](#) are to be performed

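### No pregnancy test is clearly scheduled between Cycle 1 Day 1 and end of treatment; a urine test before each cycle would be a cheap safeguard

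*Protocol*

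**What the plan says.** **Urine test.** Footnote g of Protocol Table 4 reads "On Cycle 1 Day 1 only: a urine pregnancy test will be performed prior to study drug administration". Table 3 in Section 9.5.4.3 repeats the limit in its Urinalysis category ("Urine pregnancy test (Cycle 1 Day 1 only").

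**Serum test.** Table 3 places serum β-hCG in the panel for Screening, Baseline and End of Treatment. Its Treatment Panel opens with "chloride, potassium, sodium, BUN, serum creatinine, phosphorus, calcium, albumin, total protein, alkaline phosphatase, ALT, AST, total bilirubin, CPK", then adds thyroid tests; β-hCG is not among them. Table 4 likewise marks serum β-hCG at Screening, Baseline and EOT only.

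**Table 4 marks.** The urine pregnancy row has a plain X on Day 1 under the heading for Cycles 1 to 8 (and 9 onward where applicable), and another plain X on Day 1 of Extension treatment. The legend reserves the bracketed mark for items that some cycles or some subjects may omit, and sends the reader to the footnotes.

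**General text.** Section 9.5.4.3 says "blood chemistry (including pregnancy test, as applicable), and urinalysis samples are to be obtained before study drug administration", with results reviewed at the start of each cycle. It does not say in which cycles the pregnancy test applies.

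**Related rules.** Inclusion criterion 14 asks for a repeat test if the screening result is more than 72 hours old at first dose. Criterion 16 requires highly effective contraception through the study and for 30 days afterwards. Section 9.5.7.2 requires a pregnant subject to be withdrawn.

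**The concern.** E7777 is a cytotoxic fusion protein given in repeated 21-day cycles, with no stated maximum for subjects who respond in the skin and benefit. The protocol insists on a recent negative test before the first dose and on withdrawal once pregnancy occurs. Between those two points it schedules no clear means of finding out. Contraception lowers the chance of pregnancy but detects nothing, and the Day 1 physical examination is not a test result. A woman who conceives during treatment could therefore receive further cycles before the end-of-treatment serum test.

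There is also a smaller matter of consistency: a site working from the table mark alone would test more often than a site working from the footnote.

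**Working it through.** No power or error-rate calculation applies. The check is a comparison of texts plus day counts.

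**1. Inputs.** Cycle length 21 days, five infusions per cycle, up to eight cycles (Section 9.4.1). Maximum delay 21 days for toxicity and 42 days for scheduling (Section 9.4.1.5). Last scheduled test before EOT: Cycle 1 Day 1 (footnote g).

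**2. Age of the last scheduled result at Day 1 of Cycle k**, with on-time dosing, is 21 × (k − 1) days:

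| Cycle | 2 | 3 | 4 | 5 | 6 | 7 | 8 | 9 |
|---|---|---|---|---|---|---|---|---|
| Days | 21 | 42 | 63 | 84 | 105 | 126 | 147 | 168 |

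With one maximum delay before Cycle 8: 147 + 21 = 168 days (toxicity) or 147 + 42 = 189 days (scheduling).

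**3. Share of dosing.** Cycles 2 to 8 contain 7 × 5 = 35 of 8 × 5 = 40 infusions, or 87.5%. This describes the schedule. It is not a measure of risk.

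**4. Does the plain X mean every cycle?**

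- *For:* the PK and immunogenicity row is limited to certain cycles ("A predose blood sample for immunogenicity assessment will be collected prior to dosing on Day 1 in Cycles 1, 2, 3, 5, and 8") and is bracketed on Day 1, as the legend requires. Day 8 items, required only in Cycles 1 to 3, are bracketed too.
- *Against:* the serum β-hCG row is plain, although it applies only to women. The lymph node examination row is plain on Day 1, although Section 9.5.2.2 leaves Main Study palpation to the investigator's judgment. The diagnostic blood or node sampling row is plain, although footnote c makes it conditional. The urine row itself should be bracketed on any reading, because men are not tested.

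A plain X in this table therefore does not reliably mean every cycle.

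**5. The Extension mark.** Data cutoff requires every Main Study subject to have completed Cycle 8 or to be off treatment (Section 9.1.1), and Extension treatment is for those still on treatment at cutoff. A Main Study subject treated there is already past Cycle 8. Unless cycle numbering restarts, which the protocol does not say, no Cycle 1 Day 1 occurs in the Extension. The X and its footnote are hard to reconcile.

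**6. Footnote h.** It names serum β-hCG beside LDH, followed by a parenthetical limit to screening, and then requires Day 1 laboratory results to be reviewed before dosing in each cycle. If the limit belongs to LDH alone, β-hCG could be read into Day 1 chemistry. Table 3's Treatment Panel points the other way. If the limit covers both, it disagrees with the Baseline and EOT marks for β-hCG.

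**7. After the change.** Scheduled on-treatment tests over eight cycles rise from 1 to 8. With on-time dosing, the longest scheduled interval between them falls from 147 to 21 days.

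**The case against.** The strongest reply is that the text has a settled meaning. Footnote g is attached to the row, the legend directs readers to the footnotes, Table 3 agrees, and the revision history records that Amendment 01 corrected the timing of this very test. On that view the plain X is a bracket slip, and testing every cycle is a preference that no passage requires. The protocol already demands a fresh negative test before the first dose, contraception throughout, prompt pregnancy reporting, withdrawal, and a serum test at EOT that is exempt from the waiver covering most other EOT tests. Footnote h and Section 9.5.4.3 might even be read as including β-hCG in Day 1 chemistry.

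Most of this stands as to intent: Cycle 1 only is the likelier meaning. It does not close the gap, because on that meaning nothing is scheduled between Cycle 1 Day 1 and EOT. The footnote h reading is too uncertain to count as a clear schedule. The Extension mark remains unexplained.

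A reader might go further and infer that Table 4 makes an every-cycle test mandatory, so that footnote g contradicts a requirement. The inconsistent use of brackets does not support that.

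**Conclusion.** The point holds as a minor, inexpensive safety improvement. If footnote g and Table 3 govern, no pregnancy test is clearly scheduled before Cycles 2 to 8 or later cycles. The last scheduled result is then 147 days old at Cycle 8 Day 1 with on-time dosing, and older after a delay. The table marks and footnote h need tidying whichever schedule is intended.

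This rests on reading footnote h as not adding β-hCG to Day 1 chemistry, which Table 3 supports. The documents do not give the number of women of childbearing potential, so no count of women affected can be offered. Investigators may still test when they see reason to. The ORR analysis is unaffected.

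**What to change.** Make four edits in one protocol amendment:

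1. **Footnote g**, replace the last sentence with: *For females of childbearing potential, a urine pregnancy test is done on Day 1 of every cycle, including Cycle 9 onward and the Extension Phase, and must be negative before dosing. If positive, withhold dosing and confirm by serum β-hCG; if confirmed, withdraw the subject per Section 9.5.7.2.* Later cycles need naming here because footnote a limits its rule on assessments beyond Cycle 8 to the Lead-In.
2. **Table 3**, change the urine pregnancy entry to Day 1 of every cycle, females of childbearing potential.
3. **Table 4**, bracket the Day 1 urine pregnancy mark in both the Treatment and Extension parts, since it does not apply to all subjects.
4. **Footnote h**, state that serum β-hCG is done at Screening, Baseline and EOT, and that the screening-only remark does not limit pregnancy testing.

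The Section 9.5.4.3 sentence can stay: Table 3 lists the urine test under Urinalysis, which that sentence already covers.

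The cost is 8 − 1 = 7 extra urine tests per woman of childbearing potential over eight cycles, plus one per further cycle. They fall at Day 1 visits where urine is already collected before dosing and laboratory results are already reviewed. Conceptions too recent to detect would still be missed until the next cycle.
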